7. ASSESSMENTS

7.1. Ophthalmic Examination Procedures

7.1.1. External Eye Examinations

An external eye examination will be performed to assess the general appearance of the eye. It will look at ocular motility to detect deviations from strabismus or a convergence defect.

The external eye examination will be conducted at the Screening (Visit 1) and Week 12 (Visit 6) visits, and at the Week 15 (Follow-up, Visit 7) visits if deemed necessary.

7.1.2. Direct and Indirect Funduscopy

At Screening visit, direct and indirect funduscopy will be used to look at retinal morphology (dilated eyes). Indirect funduscopy will be performed using a biomicroscope (slit lamp) and a Volk 90 diopter lens allowing evaluation of maculae and optic nerve. A 20 or 28 diopter lens can be used to evaluate the peripheral fundus and providing an overall view of the pigment epithelium. Direct funduscopy may be performed using a manual ophthalmoscope and will examine the macular ocular disc vessels, looking especially for edema and alterations of the macular reflex. Results will be collected on the Case Report Form (CRF).

Funduscopy will be conducted at Screening visit.

7.1.3. Best Corrected Visual Acuity

The best corrected visual acuity (with glasses or best possible glasses prescription) will be measured using the ETDRS charts. The letters on chart A are read using the right eye and chart B using the left eye.

The subject starts the top of the chart and begins to read down the chart. The subject reads down the chart until they reach a row where a minimum of three letters on a line cannot be read. The subject is scored by how many letters could be correctly identified.

The number of correct letters identified by each eye will be collected into the CRF.

Visual acuity will be measured at Screening (Visit 1), Baseline (Visit 2), Week 6 (Visit 5), and Week 12 (Visit 6) visits, and at Week 15 (Follow-up, Visit 7) visit if deemed necessary. The best corrected visual acuity should be obtained at each scheduled visit or repeat visit. It should not be copied from a previous visit.

7.1.4. Visual Field Test

All investigators will receive extensive training at the investigator's meeting and periodically throughout the study to improve the reliability of measurements by monitoring subject compliance and recognizing artifact in visual field examination. Investigators should repeat/reschedule sessions when subjects have poor compliance or any difficulties which interferes with visual field testing. Ophthalmologists/ VFT technician should inquire prior to testing when the subject's last seizure occurred to assess the possibility of ictal or post-ictal state to avoid interference with testing; the time of last dose of investigational product (it is

recommended that the subject withholds the morning dose of investigational product until after the VFT has been completed to reduce any potential effects of CNS events that may occur (eg, somnolence) with pregabalin which may interfere with testing). If the subject has taken the morning study dose of medication, testing should be performed when the subject is least probably affected by any potential CNS events that may occur to ensure the subject is optimally alert during the test.

Prior to performing the computerized automated perimetry (Humphrey 24-2 SITA), pupil size will be measured and recorded and must be 3 mm or greater for VFT, otherwise the pupil must be dilated. Visual fields will be measured using the Humphrey 24-2 SITA and analyzed using STATPAC according to the guidelines. A detailed guideline is provided in the [Appendix 2](#) of this document. Because visual field results are strongly affected by experience, visual field tests will be repeated on two occasions at Screening and at Baseline visits. A pre-test is recommended for all subjects who have never performed VFT.

All automated perimetry results will be read by a central reader within 3 working days of the examination. If the central reader assesses the visual field exam to be of poor quality, the exam should be repeated as soon as possible within 2 weeks of being notified. The repeat test will be performed only on the eye whose test was considered to give a poor result.

Any subject who has a new loss of sensitivity at the $p < .05$ level in five or more points in the visual field will have a repeat exam as soon as possible within 2 weeks of receiving confirmation from the central reader.

VFT will be conducted at the Screening (Visit 1), Baseline (Visit 2), Week 6 (Visit 5), and Week 12 (Visit 6) visits as well as at the Week 15 (follow-up, Visit 7) visit if deemed necessary.

If a subject complains about their vision at the site it should be recorded as an adverse event like every other adverse event regardless of central reading.

If the subject does not complain about the vision and the central reader shows confirmed deterioration based on the VFT this should not be collected as an adverse event because this is the study endpoint.

7.2. Clinical Laboratory Tests

Laboratory

The following safety laboratory tests will be performed at the Screening (Visit 1) and Week 12 (Visit 6).

Safety Laboratory

Hematology	Chemistry	Urinalysis	Other
Hemoglobin	Creatinine	PH	Urine Pregnancy test ^a
Hematocrit	BUN	Color	Urine drug testing ^c
RBC Count	Glucose	Clarity	(amphetamines,
Platelet Count	Ca ⁺⁺	Specific gravity	antidepressants,
WBC Count	Na ⁺ , K ⁺ , Cl ⁻	Glucose (qual)	barbiturates,
	Total CO ₂	Protein (qual)	benzodiazepines,
	(Bicarbonate)	Blood (qual)	canabinoids, cocaine,
	AST, ALT	Ketones	methadone,
	Total Bilirubin	Nitrites	methaqualone,
	Alkaline phosphatase	Microscopy ^b	opiates,
	Uric acid		phenothiazines,
	Albumin		propoxyphene and
	Total protein		alcohol)
	Creatine phosphokinase		

^a Childbearing potential females only.
^b Only if urine dipstick is positive for blood or protein.
^c Only at Screening.

Results of the urine drug tests at screening (V1) must be negative for the subject to receive trial medication on Day 1.

- Safety laboratory tests from Screening must have no clinically significant findings, as judged by the investigator, in order for a subject to receive trial medication on Day 1.
- CL_{cr} (must be >60 ml/min) will be estimated from serum creatinine at screening to determine eligibility using the equations that follow.¹³

$$\text{Male } \text{CL}_{\text{cr}} = \frac{(140 - \text{age}) \times \text{Body Weight (kg)}}{72 \times \text{Serum Creatinine}}$$

$$\text{Female } \text{CL}_{\text{cr}} = \left[\frac{(140 - \text{age}) \times \text{Body Weight (kg)}}{72 \times \text{Serum Creatinine}} \right] \times 0.85$$

In order to use SI units for creatinine ($\mu\text{mol/L}$), use the following formulas:

$$\text{Male } \text{CL}_{\text{cr}} \text{ (mL/min)} = \frac{(140 - \text{age}) \times \text{Body Weight (kg)}}{\text{Serum Creatinine}} \times 1.23$$
$$\text{Female } \text{CL}_{\text{cr}} \text{ (mL/min)} = \left[\frac{(140 - \text{age}) \times \text{Body Weight (kg)}}{\text{Serum Creatinine}} \right] \times 1.23 \times 0.85$$

7.3. Vital Sign, Body Weight and Physical Examination

Vital signs (sitting heart rate and blood pressure) will be obtained at Screening (Visit 1), Baseline (Visit 2), Week 1 (Visit 4), Week 6 (Visit 5), Week 12 (Visit 6) and Early Termination (ET). BP will be measured with the subject's arm supported at the level of the heart, and recorded to the nearest mm Hg. The same arm (preferably the dominant arm) will be used throughout the trial. BP and heart rate will be measured after at least 5 minutes in sitting position. When done manually, heart rate will be measured in the brachial/radial artery for at least 30 seconds. The use of automated devices for measuring BP and heart rate are also acceptable. Any clinically significant negative changes (increase or decrease) in vital signs from the entry examination should be recorded as an adverse event and/or based on the clinical judgment of the PI.

Body weight will be collected at Screening (Visit 1), Baseline (Visit 2), Week 1 (Visit 4), Week 6 (Visit 5), Week 12 (Visit 6), Week 15 (Visit 7) and Early Termination (ET). Any clinically significant negative changes (increase or decrease) from the entry examination should be recorded as an adverse event for weight and/or based on the clinical judgment of the PI.

To reduce measurement variability of body weight, subjects should be weighed on the same scale at each visit that body weight is assessed; should not carry extraneous items such as purses, blackberries, and cell phones onto the scale; should remove their coats and shoes before being weighed, and should empty their pockets of any heavy items.

A physical exam will be performed at Screening (V1) and Week 12 (Visit 6). Items included will be:

- General appearance – including height (at Screening only);
- Skin – Examination for the presence of rash;
- HEENT – Examination of extraocular movements, pupillary response, determination of nystagmus, and visual field examination by confrontation;
- Lungs and Cardiovascular – Auscultation of lung fields, determination of BP, cardiac rhythm and rate auscultation for the presence of murmurs, gallops, or rubs;
- Neurologic – Including mental status, station and gait, cranial nerves, motor and sensory function, reflexes, and coordination;
- Abdominal – Palpation and auscultation performed.

Additional physical assessment will be made as necessary to evaluate symptoms or adverse experiences at the discretion of the investigator. Any clinically significant negative changes on the physical examination from the entry examination should be recorded as an adverse event and/or based on the clinical judgment of the PI.

7.4. Electrocardiogram (ECG)

A 12-lead ECG (singlet) will be performed at Screening (Visit 1). ECG should be performed after the subject has rested quietly for at least 10 minutes in a supine position. ECG tracing will be evaluated by the investigator in a real time for the safety monitoring of the subjects. In some cases, it may be appropriate to repeat abnormal ECGs to rule out improper lead placement as contributing to the ECG abnormality. It is important that leads are placed in the same positions each time in order to achieve precise ECG recordings.

7.5. Assessment of Suicidal Ideation and Behavior

Three tools are being used to assess for suicidal ideation and behavior during the study; the Sheehan-Suicidality Tracking Scale (S-STS), the Columbia-Suicidality Severity Rating Scale (C-SSRS) and the Suicidal Behaviors Questionnaire – Revised (SBQ-R). Subjects randomized prior to Amendment 4 will only complete the S-STS.

7.5.1. Sheehan-Suicidality Tracking Scale (S-STS)

The Sheehan-Suicidality Tracking Scale (S-STS) is an 8-item prospective rating scale that tracks treatment-emergent suicidal ideation and behaviors. This scale was adapted from the Suicidality Module of the Mini International Neuropsychiatric Interview (MINI) Structured Diagnostic Interview for DSM-IV. Items 1a, 2-6, 7a, and 8 are scored on a 5-point Likert scale (ranging from 0= not at all to 4=extremely). Items 1, 1b, and 7 require yes or no responses. This scale can be administered either by a clinician (ie, MD or a PhD level clinical Psychologist) or patient through self-report. The baseline Lifetime Assessment will be completed at Screening and the “Since Last Visit” version will be completed at Baseline (Visit 2), Randomization (Visit 3), Week 1 (Visit 4), Week 6 (Visit 5), Week 12 (Visit 6), Week 15 (Visit 7) and ET.

Subjects randomized prior to Amendment 4 will complete the S-STS and not the C-SSRS or SBQ-R. Subjects enrolled/randomized after implementation of Amendment 4 will not complete the S-STS but will instead complete the C-SSRS and SBQ-R.

7.5.2. Columbia-Suicidality Severity Rating Scale (C-SSRS)

The Columbia-Suicidality Severity Rating Scale (C-SSRS) is a semi-structured interview developed in the National Institute of Mental Health Treatment of Adolescent Suicide Attempters Study to assess severity and track suicidal events through any treatment.¹⁴ The C-SSRS is being used in the current study to provide a summary measure of suicidal risks. This scale is to be completed by a trained clinician. Training materials on the scale will be provided to investigator sites by Pfizer. The Lifetime version is completed during the first visit and the Since Last Visit version will be completed at subsequent visits.

7.5.3. Suicide Behaviors Questionnaire – Revised (SBQ-R)

The SBQ-R is a 4-item; self-report questionnaire that assesses behaviors associated with suicidality. The SBQ-R will be completed at Screening (V1) following implementation of Amendment 4. Subjects screened under Amendment 3 but continue under Amendment 4 should complete the SBQ-R at the baseline or randomization visit.

7.5.4. Patient Health Questionnaire-8 (PHQ)

The PHQ-8 is a self-administered version of the PRIME-MD diagnostic instrument for common mental disorders. The PHQ-9 is the depression module, which scores each of the 9 DSM-IV criteria as 0 (not at all) to 3 (nearly every day).¹⁵ The PHQ-8, a validated subset of the PHQ-9, which comprises the first 8 items of the measure, will be completed by subjects at Screening (Visit 1).

The score is the sum of items 1-8. A total score ≥ 15 indicates significant depression and requires mental health risk assessment.¹⁶

When scoring the PHQ-8, if more than one response is given on an item and two consecutive numbers are checked, score the higher (more distress) number; however, if the numbers are not consecutive, do not score the item. If more than 1 item is missing, the PHQ-8 should be reported as Not Done.

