Patient assessment of seizure frequency						X	

Protocol Activity	Screening	Baseline	Wk 0 Randomization	Wk 1	Wk 6	Wk 12 (Or ET)	Week 15 (Follow-Up)
Investigational product Dispensing			X ^{i,j}	X ^k	X ^k	X ^j	
Dispense Dosing Diary			X		X		
Review Dosing Diary with subject				X	X	X	X
Sheehan-Suicidality Tracking Scale (S-STSS) ^{o,r}	X	X	X	X	X	X	X
Columbia-Suicide Severity Rating Scale (C-SSRS) ^{o,r}	X	X	X	X	X	X	X
Suicidal Behaviors Questionnaire – Revised (SBQ-R) ^r	X						
Patient Health Questionnaire–8 (PHQ-8)	X						
Assessment of need to complete a risk assessment ^q	X	X	X	X	X	X	X
Adverse Events Report			X			X	

- a. Subjects who have not had a test within 2 years. See inclusion criteria 1.
- b. Subjects who have not had a test within 3 years. See inclusion criteria 4.
- c. Hemoglobin, hematocrit, RBC count, WBC count, platelet count.
- d. Electrolytes (Na, K, Ca, Cl, bicarbonate), creatinine, BUN, glucose, AST, ALT, alkaline phosphatase, bilirubin, CK, uric acid, albumin, total protein.
- e. Specific gravity, PH, Glucose (qual), Protein (qual), Blood (qual), Ketones, Nitrite and Microscopy if urine dipstick is positive for blood or protein.
- f. Childbearing potential female subjects only.
- g. Subjects who have had visual findings on Week 12 and subsequently confirmed.
- h. A repeat may be necessary upon the confirmation from central reader.
- i. Recommend subject to take first dose in the evening.
- j. Titration/tapering dose.
- k. Treatment dose.
- l. Conduct 2 tests.
- m. Usually occur between the 3rd – 7th day after Baseline (Visit 2) when the verification of VFT is available.
- n. Screening procedures can be completed within 21 days prior to Baseline; Study Visits 4 – 7 have a ±3 days window.
- o. The “Lifetime” assessment is completed at Screening and the “Since Last Visit” assessment is completed at **all** other visits.
- p. Including neurological exam at screening.
- q. A risk assessment must be performed and documented if the subject meets the criteria detailed in Protocol.
- r. Subjects screened/randomized under Amendment 3 will continue the S-STSS for assessment of suicidal ideation and behaviour. Subjects screened /randomized under Amendment 4 will have suicidal ideation and behaviour assessed by the C-SSRS and the SBQ-R.

TABLE OF CONTENTS

SCHEDULE OF ACTIVITIES.....	7
LIST OF TABLES	12
APPENDICES	12
1. INTRODUCTION	13
1.1. Background	13
1.2. Rationale.....	14
2. TRIAL OBJECTIVES AND ENDPOINTS	14
2.1. Objective	14

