7.5.5. Assessment of Suicidal Ideation and Behavior During Screening

The Investigator will review the results of the STS (Lifetime), C-SSRS (Lifetime), SBQ-R, PHQ-8 and medical history. The following criteria would indicate a potential risk:

- Positive subject's responses (score ≥ 1) on any of these S-STS questions:
 - 1a (To what extent did you plan or intend to hurt yourself?),
 - 1b (Did you intend to die as a result of this accident?),
 - both 3 and 4 (How seriously did you ever want to harm yourself or to hurt or to injure yourself? and Did you think about suicide?),
 - 5 (How seriously did you ever plan for a suicide?),
 - 6 (How seriously did you ever take active steps to prepare for a suicide attempt in which you expected or intended to die?),
 - 8 (How seriously did you ever attempt suicide?).
- Suicidal ideation associated with actual intent and/or method and/or plan in the past year based on C-SSRS assessment (ie, 'yes' response to C-SSRS items 4 (Active suicidal ideation with some intent to act, without specific plan) or 5 (Active suicidal ideation with specific plan and intent)).

- Any previous history of suicidal behaviors reported or documented within the past 10 years.
- For events that occurred within the past 10 years, an answer of “yes” to any of the suicidal behavior items of the C-SSRS.
- SBQ-R total score ≥ 8 .
- Clinically significant depression: PHQ-8 total score ≥ 15 .
- The presence of any current major psychiatric disorder that is not explicitly permitted in the inclusion/exclusion criteria.
- In the investigator’s judgment a risk assessment or exclusion is required.

If any of these criteria are met and the subject is being considered for study participation, a risk assessment must be completed to determine whether it is appropriate for the subject to be enrolled.

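### A screening PHQ-8 with two or three missing items is reported as Not Done even when the answered items already reach 15, so it misses the mandatory risk-assessment trigger (minor, entry safety only)

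*Protocol*

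**What the plan says.** Protocol 7.5.4 has the subject complete the PHQ-8 at Screening, with items scored from 0 to 3. On scoring it says "The score is the sum of items 1-8", and that a total of 15 or more "indicates significant depression and requires mental health risk assessment". An item can be lost in two ways: the subject leaves it blank, or marks two answers that are not adjacent, in which case the instruction is "however, if the numbers are not consecutive, do not score the item". For incomplete forms the rule is "If more than 1 item is missing, the PHQ-8 should be reported as Not Done".

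Protocol 7.5.5 lists the screening criteria for potential risk. The PHQ-8 entry begins "Clinically significant depression: PHQ-8 total score", with a cut-off of 15. If any listed criterion is met and the subject is still being considered for the study, "a risk assessment must be completed to determine whether it is appropriate for the subject to be enrolled". Neither section makes an exception for an incomplete form whose answered items already reach 15.

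**The concern.** The Not Done rule makes sense when the missing items leave the total in doubt. Here it also applies where there is no doubt. An item cannot score below 0, so once the answered items reach 15 the full total is at least 15 whatever the missing answers would have been. Such a form passes the protocol's own depression cut-off and yet, on the wording, has no total with which to meet the criterion.

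What is at stake is safety at entry. A subject whose answers already show significant depression by the protocol's definition would not trigger the mandatory risk assessment through the PHQ-8. The assessment would then depend on another criterion or on the investigator's judgment. The PHQ-8 is given only at Screening, and the in-trial triggers in 7.5.6 use only the S-STS and C-SSRS, so no later PHQ-8 would pick the case up.

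**Working it through.** The plan states no figure on this point to reproduce. The check is a full count of answer patterns.

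**Inputs (Protocol 7.5.4 and 7.5.5).** Eight items, each 0, 1, 2 or 3; score = sum; cut-off 15; Not Done if more than one item is missing.

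**Step 1: where can it happen?** With *m* items missing, the largest possible answered sum is 3 × (8 − *m*).

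| Items missing | Items answered | Largest answered sum | Can reach 15? |
|---|---|---|---|
| 2 | 6 | 18 | yes |
| 3 | 5 | 15 | yes, only if all five are 3 |
| 4 | 4 | 12 | no |

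Among Not Done forms, the problem therefore arises with exactly two or three missing items. With two missing, the six answers must average at least 15/6 = 2.5; with three missing, all five must be 3.

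**Step 2: how many patterns?**
- Two missing: 4^6 = 4096 patterns. Sum 18: 1; sum 17: 6; sum 16: 21; sum 15: 56. Total 1 + 6 + 21 + 56 = 84, and 84/4096 = 2.1%.
- Three missing: 4^5 = 1024 patterns. Sum 15: 1, and 1/1024 = 0.1%.
- Four missing: 0 of 4^4 = 256.

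**Step 3: would acting on the answered sum ever be wrong?**
- Two missing: each of the 84 patterns can be completed in 4^2 = 16 ways, so 84 × 16 = 1344 completed forms. Their totals run from 15 + 0 = 15 to 18 + 6 = 24.
- Three missing: 1 × 4^3 = 64 completed forms, with totals from 15 + 0 = 15 to 15 + 9 = 24.

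None of the 1344 + 64 = 1408 completed forms falls below 15. Counting these forms as meeting the criterion gives no false triggers.

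The percentages weight every answer pattern equally. They show how narrow the case is and do not estimate how many subjects are affected.

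**The case against.** The strongest reply is that Not Done is a rule for recording the score and does not tell the investigator to ignore the answers. Section 7.5.5 has the investigator review the PHQ-8 results, and one of its criteria is that in the investigator's "judgment a risk assessment or exclusion is required". An investigator would have to see six answers averaging at least 2.5, or five answers all at 3, and do nothing.

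Other points support the reply:
- Section 6.1 already lists the PHQ-8 among the procedures to be completed at screening, and there is time to return the form: "Screening procedures can be completed within 21 days prior to Baseline" (Schedule of Activities, footnote n).
- Section 4.2 excludes significant psychiatric disorder and, under stated conditions, recurrent severe depression. It also excludes subjects whom the investigator judges to be at risk of suicide or self-harm.
- A current major psychiatric disorder that is not expressly permitted is a separate 7.5.5 trigger.
- The S-STS, or the C-SSRS with the SBQ-R, asks about suicidality directly.
- Section 6.2.2 has the need for a risk assessment determined again before randomization.
- The protocol cites an instruction manual for the PHQ-8, which may deal with incomplete forms and is not available here.

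Much of this stands, and it is why the point is minor. None of it makes a Not Done form meet the PHQ-8 criterion. The Not Done sentence sits in the scoring paragraph, and the criterion is worded on the score. Judgment permits an assessment; at 15 or more the protocol otherwise makes it mandatory. Sections 6.2.1 and 6.2.2 name catch-up steps for the C-SSRS Lifetime and the SBQ-R (at least the SBQ-R step serves subjects moving from Amendment 3 to 4), but none for the PHQ-8. The other scales in 7.5.5 address suicidal ideation and behavior; the PHQ-8 is the only depression scale listed.

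**Conclusion.** The concern holds, at the lowest severity. On the current wording, a PHQ-8 with two or three missing items and an answered sum of 15 or more is certain to be above the cut-off and still does not meet the 7.5.5 PHQ-8 criterion. This covers 84 of 4096 patterns with two items missing and 1 of 1024 with three.

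The conclusion rests on reading Not Done as leaving no total score. How many subjects are affected cannot be derived, because the documents give neither a rate of incomplete forms nor the distribution of scores. The gap concerns the mandatory trigger only; nothing prevents a risk assessment on other grounds. SAP 8.2.3.3 summarizes the PHQ-8 descriptively by question, so no endpoint, analysis set or power figure changes. The scope for benefit is also limited: Protocol 9.1 cites 187 enrolled subjects, and Section 3 plans for about 187.

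**What to change.** 1. In 7.5.4 and 7.5.5, state that answered items summing to 15 or more meet the PHQ-8 criterion, however many items are missing. Keep the cut-off of 15, and keep the Not Done rule for all other forms with more than one missing item.
2. In 6.1, have the site check the form and return blank or unscorable items to the subject within the existing screening window.
3. If screening is closed, look through the item data of Not Done forms for answered sums of 15 or more, and tell the investigator of any found.

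The cost is one sentence in each of the three sections and a short form check. Item 1 may add risk assessments. Their number cannot be computed from the documents, but every one would be in a subject whose full total would be 15 or more. If screening is closed, only item 3 is useful.
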